1 BACKGROUND AND RATIONALE

1.1 Inflammatory Bowel Disease:

The purpose of this protocol is to study the safety and tolerability of MSCs for the treatment of pediatric and young adult patients with moderate to severe Inflammatory Bowel Disease (IBD), including Crohn's disease (CD) and ulcerative colitis (UC), which is unresponsive to conventional therapy. CD and UC are chronic inflammatory diseases characterized by relapsing inflammation of the gastrointestinal tract. There is no known cure for these lifelong conditions. CD affects the full thickness of the bowel wall, and may affect the different areas of the small and large intestine. Conversely, UC affects only the large intestine.

IBD in children profoundly affects nutrition, growth, education, employment, and social well-being. The prevalence of CD in people < 20 years of age is 43 per 100,000 and for UC is 28 per 100,000 in the US. Overall, the cost associated with IBD care is greater in children than in adults. This likely reflects the high number of incident cases in children, but also likely reflects the increased severity of IBD in children. [5] Though a much lower prevalence is found in other areas of the world, IBD appears to be emerging in areas such as China, South Korea, India, and Iran, correlating with industrialization and westernization. [6] Twenty-five to 30% of all patients with CD and 20% of those with UC are diagnosed before age 20. [7] [8]

Although exact details of the disease pathogenesis are unknown, the generally accepted hypothesis is that IBD occurs as an exaggerated and dysregulated mucosal immune response to environmental factors, including intestinal microbiota, in a genetically susceptible host. The hallmark of IBD is an infiltration of innate immune cells (neutrophils, macrophages, dendritic cells, and natural killer T cells) and adaptive immune cells (B cells and T cells) into the intestinal lamina propria. Innate immune cells provide a rapid response to microbes via sensors (i.e. toll-like receptors) which recognize microbial and nonmicrobial triggers and initiate inflammatory responses. In CD, failure of dendritic cells to induce tolerogenic regulatory CD4+ T cells leads to a cascade of intestinal inflammation. [9] CD is characterized by an imbalance of elevated pro-inflammatory effector T cells (Th17 and Th1 cells secreting cytokines interleukin-17 and 22, interferon γ and TNF α) and decreased inflammatory-suppressing regulatory T cells. [10, 11] Th2 cytokines secreted by natural killer T cells are implicated in UC. [12] [10]

1.2 Current Standard IBD Treatment:

Treatment goals in pediatric IBD include improving quality of life, maximizing growth and nutrition, and preventing complications, such as toxic megacolon, anemia, intra-abdominal abscess, intestinal obstruction, intestinal perforation, growth failure and

pubertal delays. In spite of advances in IBD therapeutics, a significant number of patients continue to have symptoms while on conventional medications. Moderate to severe IBD is treated with systemic corticosteroids, immunomodulators (6-mercaptopurine for CD and UC, methotrexate for CD), and biologics (i.e. infliximab, adalimumab, certolizumab). These medications are variably effective and have potential for severe complications and side effects. From the first introduction of corticosteroids, 20% of patients do not respond, and 35% of the responders develop steroid dependency. [13, 14] 6-mercaptopurine and its parent drug azathioprine possess well-known immunosuppressive and lymphocytotoxic properties. [15] While 50% of patients will achieve a clinical response after 4 months of therapy, only 40-65% of patients maintain remission, and the onset of these drugs is slow. [16, 17] Methotrexate is effective in about a third of patients with CD, although experience with methotrexate in pediatric IBD literature is scant and retrospective. [18] Toxicities, particularly teratogenicity in females, limit its use. Methotrexate may also cause nausea, bone marrow suppression, infections, and liver injury.

Biologic therapies are widely used for treating both UC and CD. Established and emerging therapies for IBD are directed toward the destruction or deterrence of activated effector T cells, or blockade of Th1-driving cytokines. Trials with anti-cytokine therapy, in particular anti-TNF α medications, have been successful for patients with refractory disease. There are 4 anti-TNF monoclonal antibodies currently FDA approved for use in adults with IBD: infliximab, a chimeric IgG1 antibody; adalimumab, a fully humanized IgG1 antibody; certolizumab and golimumab, both PEGylated humanized Fab' fragments. [19] However, there are fewer options for pediatric patients, as only infliximab is FDA approved for pediatric UC, while both adalimumab and infliximab are indicated for treatment of pediatric CD. Despite these advances, one third of patients do not respond to these medications, and an additional third subsequently lose response or become intolerant. [20, 21]

Safety data from the use of TNF inhibitors highlight concerns regarding risk of infections, such as tuberculosis, listeria, pneumocystis, and invasive fungal organisms. It is known that concomitant use of immunomodulators improves clinical efficacy of infliximab in adults. [22, 23] However, serious risks are associated with infliximab and immunomodulators. In addition to infection, include infusion/injection reactions, hepatitis, and an otherwise extremely rare and almost uniformly fatal hepatosplenic T-cell lymphoma in pediatric and young adult CD patients receiving the combination of infliximab and 6MP or azathioprine. [24, 25] Thus, a need for new therapies for refractory pediatric IBD exists, particularly the need for safely modulating the immune system to reduce or reverse the abnormal inflammatory cascade.

1.3 Description of the Study Agent/Intervention

Human Mesenchymal Stromal Cells (MSCs) - “Universal Stem Cells”

MSCs are undifferentiated, non-hematopoietic, pluripotent cells that give rise to mesodermal tissue types, including bone, cartilage, tendon, muscle, and fat. [26] MSCs provide support for the growth and differentiation of hematopoietic progenitor cells in bone marrow microenvironments and, in animal models, promote engraftment of hematopoietic cells. [27] These cells may be isolated from most human tissues, usually bone marrow, and expanded *ex vivo*. [28, 29] MSCs do not express the hematopoietic markers CD45, CD34, and CD14, or the co-stimulatory molecules B7-1, B7-2, CD40, CD40 ligand, CD80 and CD 86 and probably therefore do not activate alloreactive T cells. [30-32]. Minimal classification criteria has been defined as positive for CD146, CD90, and human leukocyte antigen (HLA) class 1 and negative for hematopoietic cell markers. [33] MSCs constitutively express HLA class I molecules, but do not express class II molecules on the cell surface. In the presence of inflammatory cytokines, i.e. IFN γ and TNF α , the surface expression of class I is increased and class II expression is induced. [32] However, mesenchymal tissues, such as bone and cartilage have been successfully transplanted without the need for donor-recipient MHC matching, and the incidence of acute rejection of these tissues is low. Thus, the mesodermal origin of BMSCs, along with lack of co-stimulatory molecules necessary to activate T cells, suggests low immunogenicity of these cells. MSCs isolated from humans and other mammalian species do not elicit a proliferative T cell response from allogeneic lymphocytes. [34, 35]

MSCs have been shown to possess immunomodulatory properties, following the initial observation that bone marrow-derived MSCs suppressed T cell proliferation. [36] As expected, MSCs suppress proliferation of allogeneic T cells in a dose-dependent, non-HLA-restricted manner. [30, 32, 37] MSCs inhibit the division of stimulated T cells by preventing their entry into the S phase of the cell cycle and by mediating irreversible B0/G1 phase arrest. [38] MSCs interact with other immune cells and are capable of altering immune cell responses. MSCs can inhibit the differentiation of monocytes into immature dendritic cells.[39] MSCs also impair the ability of DCs to express co-stimulatory molecules, produce cytokines, and stimulate T cells. [40] MSCs can decrease the pro-inflammatory potential of dendritic cells by inhibiting their production of tumor-necrosis factor (TNF) and IFN- γ .[41] MSCs increase production of IL-10, thereby limiting T cell expansion. [41] Suppression of T cell responses is in part mediated by incompletely defined soluble factors, and MSCs may also suppress T cell reactivity by inducing T regulatory cells. [42]

A critical benefit of MSCs is that they do not seem to induce immunological memory in the recipient even when they are completely HLA mismatched, to the point of avoiding rapid rejection. [43] Given the goal of healing intestinal mucosa, another possible benefit of MSCs is that they have been shown to promote tissue repair and healing after radiation injury. Infused MSCs improve the outcomes of acute renal, neural, and lung injury, perhaps leading to a switch from pro-inflammatory to anti-inflammatory cytokines

at the site of injury. [44] Thus, much research has been focused on the potential use of MSCs for the treatment of chronic wounds, degenerative diseases, autoimmune diseases, and graft-versus-host disease. [45-48] The vast majority of studies of MSCs have been performed in adults.

1.4 Scientific Rationale and Clinical Justification

1.4.1 Rationale for the study of BMSCs in Pediatric IBD

Pediatric IBD is a chronic, life-long condition beginning in childhood, characterized by relapsing inflammation of the gastrointestinal tract. Inflammation is thought to be mediated by T cells, macrophages, and dendritic cells that produce downstream cytokines. Despite the many therapeutic advances in the treatment of IBD, many patients still suffer with refractory disease. Children with IBD are typically exposed to multiple medications over years, and many suffer with associated serious side effects.

According to 2009 US Census data, inflammatory bowel diseases (IBD) (i.e. Crohn's disease and ulcerative colitis) affect about 1.2 million Americans. Of these, 62,000 are children (38,000 CD and 23,000 UC). Thus, 5% of all IBD cases in the USA are of pediatric age (<20 years). This qualifies drugs to treat pediatric UC and pediatric CD as orphan indications.

(http://www.accessdata.fda.gov/scripts/opdlisting/oopd/OOPD_Results_2.cfmIndex_Number=340911) Further, while there are options for the treatment of IBD in adults, other than corticosteroids, infliximab (Remicade) and adalimumab (Humira) are FDA-approved for the treatment of moderate to severe pediatric CD. Infliximab has orphan drug designation to treat pediatric UC. Certolizumab pegol, methotrexate, 6MP, and 5-ASA products are NOT FDA approved for use in children with UC or CD.

(<http://www.accessdata.fda.gov/scripts/cder/drugsatfda/>)

The scientific rationale for investigating the use of MSCs in IBD patients is based on known properties of inflammatory and immune modulation and enhancement of tissue repair. This is not a first-in-human study and there is now a sizable body of evidence that this intervention is safe when used in people ≥ 18 years of age. However, the safety of MSCs has not been yet demonstrated in children with IBD. While children cannot be treated as "small adults", this is not an intervention that is expected to have substantially different impact on children than adults because metabolic differences are not a concern for this intervention. CD and UC are considered similar enough that efficacy in children has been extrapolated from adults in past trials of drugs used to treat IBD.

Therefore, there is an urgent medical need to evaluate novel therapies such as MSCs in pediatric IBD since:

- 1). Children with refractory IBD have few well-studied treatment options.
- 2). MSC therapy has already been evaluated in adults

BMSCs

3). There is not only the potential for benefit when using MSC in IBD but also the high likelihood that the allogeneic MSC will not cause the systemic immune suppression seen with other investigational therapies for this disease.

The MSCs that we propose using are different because they are passaged fewer times (up to 4 passages). One of the limitations when expanding MSCs is the time, labor, necessary space and costs associated with the expansion of these cells. For example, to generate 500 million MSCs using standard T-175cm² flasks requires four-five passages and as many as 200 flasks by the final passage. One way to circumvent these limitations is to use a functionally-closed, automated bioreactor that expands a large number of cells in a short period of time, such as the Quantum Cell Expansion system. Besides being a closed system (which limits the chance of contamination), the bioreactor requires only about 20% of the labor that the normal flask-based expansion requires and manufactures the cells 1-2 weeks sooner. In addition, the Quantum can produce 200-400% more cells during the same time period. In [name] preliminary pre-clinical studies, >500 million MSCs can be expanded after only two passages with the potential to generate over 1 billion MSCs by passage two, and over 2.5×10^{10} MSCs by passage three. In these same studies, cells obtained from the Quantum had a similar phenotype to those expanded in flasks. We are one of the few centers with a Quantum system. [name] is an established expert in the manufacturing of MSCs for phase 1 trials, as well as the Director of the GMP facility at CNHS. [49, 50]

Our cell therapy product consists of allogeneic mesenchymal stromal cells manufactured from an eligible normal donor. We have a CNMC IRB-approved protocol (Pro00006717) that provides a mechanism for the use of excess bone marrow obtained from healthy donor bone marrow harvests. Up to 100 mL of marrow will be obtained from Lonza (Walkersville, MD) under informed consent and transported to Children's National Health System in a validated process at 2-8°C. The donor will meet the eligibility requirements as described in 21 CFR parts 1271 Subpart C. Testing (Table 1) will be performed using FDA-approved, cleared and/or licensed kits by Lonza within 7 days of collection of the marrow for manufacturing. Manufacturing will commence within 24 hours of marrow collection. Risk factors will be assessed by taking a clinical history, clinical examination, and by use of a standard questionnaire for blood donors.

Table 1:	Test
Chagas Disease	
Hepatitis B Surface Antigen	
Hepatitis B Core	
Hepatitis C Core	
HIV 1 and 2	
TAQ Screen MPX (HBV, HCV, HIV-1 group M RNA, HIV-1 Group O)	
NAT HCV	
NAT West Nile Virus	
Serological Test for Syphilis	
CMV	
HTLV-1	

This would not be a first-in-human study and there is now a sizable body of evidence that this intervention is safe when used in people ≥ 18 years of age. However, the safety of MSCs has not been yet demonstrated in

children with IBD. Safety and dosing may not be extrapolated from adult studies, as classic pharmacokinetic monitoring to document equivalent exposure-response is not feasible with cell therapies.

1.4.2 PLAN OF STUDY:

This is a pilot phase 1 treatment protocol for subjects with moderate to severe CD or UC who have failed or are intolerant of one biologic. Subjects must have had a flexible sigmoidoscopy or colonoscopy or MR enterography within 2 months of enrollment, demonstrating active inflammatory bowel disease. Subjects with moderate to severe CD are defined differently in children and adults. In patients <17 years of age, moderate to severe CD will be defined as having a Pediatric Crohn Disease Activity Index (PCDAI) score of > 30 (range 0-100) and subjects with moderate to severe UC are defined as a patients with a Pediatric Ulcerative Colitis Activity Index (PUCAI) score of >34 (range 0-85). In patients \geq 18 years of age, moderate to severe CD will be defined as a CDAI of \geq 220 (range 0-600), and moderate to severe UC defined as a Mayo score of \geq 6 (range 0-12). In our study, at the specification of the FDA IND review, a young adult cohort will be enrolled first and monitored for toxicity. A pediatric cohort will only begin to enroll if there are no serious adverse events observed in the young adult cohort. Subjects will be closely monitored both by the study team to detect and evaluate adverse events (AEs), serious adverse events (SAEs), and toxicity requiring discontinuation of the intervention.

Three young adult patients (ages $17 \leq 22$ years) will be enrolled, staggered by at least 7 days. A fixed dose will be studied: 1×10^6 cells/kg administered intravenously (IV) weekly for 4 consecutive weeks. Infusions are administered over the first 28 days, followed by a 45 day monitoring period. Our chosen dose (1×10^6 cells/kg weekly for a duration of 4 weeks) is within the dosing parameters of previous trials. In trials of MSCs in pediatric GvHD, doses as high as 8×10^6 cells/kg/dose were given up to twice per week for four weeks. [51] The rate of administration (for patients < 35 kg, total infusion over 60 minutes, and for ≥ 35 kg, 4-6 ml/minute via infusion pump) is also consistent with prior pediatric administration in patients with GvHD. [51]

In our study, toxicity will be scored as a binary variable indicating occurrence or non-occurrence over a monitoring interval from the start of MSC therapy to 45 days after the last infusion. Based on the planned administration schedule, the total toxicity monitoring period will have duration $28 + 45 = 73$ days. If we observe no severe (grade 3 or worse) adverse events in the young adult cohort, we will wait a minimum of 45 days before beginning to enroll 3 more patients, ages $12 \leq 16$ years (pediatric cohort). If we observe a severe (grade 3 or worse) adverse event occurring at any time from the start of therapy to 45 days following the last MSC administration in the young adult cohort we will stop the study. If we observe no SAEs attributed to MSC administration in the young adult cohort but an SAE (grade 3 or worse) occurring at any time from the start of therapy to 45 days following the last MSC administration in the pediatric cohort, we will stop the study. If patients with active disease do not have >grade 2 toxicity attributed to

cells and fail to rapidly progress with disease requiring urgent therapy or surgery, and at the discretion of the principal investigator, 4 additional weekly doses may be administered. Subjects are eligible to receive up to 4 additional doses of MSCs at weekly intervals, each of which will consist of the same cell number (1×10^6 cells/kg). The safety assessment period will be 45 days from the last dose administered. A maximum of 6 patients will be enrolled. Assuming an accrual rate of 3-4 patients per year, it is anticipated that it may require at least 18- 24 months to accrue all 6 patients. With the additional 24 months of follow up to evaluate longer-term safety and efficacy endpoints, the anticipated trial duration will be about 48 months.

The primary study endpoint is safety and tolerability of the administration of human allogeneic bone marrow-derived MSCs to children and young adults with IBD, measured by the frequency of any SAEs, AEs and/or early treatment discontinuations. Secondary endpoints will include: 1) magnitude of change in clinical indices CDAI, Mayo, PCDAI and PUCAI) relative to baseline, reporting the average decline and 95% confidence limit; 2) changes in biomarkers (i.e. C-reactive protein, fecal calprotectin, anti-HLA antibodies and viral specific T-cell activity.) and 3) where available, magnitude of endoscopic improvement, as assessed by change in endoscopic scores (Simple Endoscopic Score Crohn's Disease [SES-CD] for CD or Endoscopic Sub Score within the Mayo Score for UC) relative to baseline, reporting the average decline and 95% confidence intervals [3, 4].

We will collect serum, saliva, peripheral blood mononuclear cells, stool, and urine for study of known and potential biomarkers of disease response. A potential concern regarding this therapy is the effect upon T cell-mediated immunity. Thus, we will assess peripheral viral-specific T cell activity before and after therapy.

The trial has been registered at clinicaltrials.gov (#NCT02150551). The IND has been reviewed and approved at the Center for Biologics Evaluation and Research at the FDA (IND#15902).

Safety and dosing may not be extrapolated from other populations, and classic pharmacokinetic monitoring is not feasible with cell therapies. A young adult cohort will be enrolled and monitored for toxicity. A pediatric cohort will only begin to enroll if there are no serious adverse events observed in the young adult cohort. Subjects will be closely monitored both by the study team and an independent DRC to detect and evaluate adverse events, serious adverse events, and toxicity requiring discontinuation of the intervention. Participants will be followed closely with weekly follow-up and assessment during the treatment protocol, and a subsequent 45 day follow up period after last MSC infusion. Laboratory and clinical data will be collected per protocol.

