3.6 Table 1: Protocol of Events

Visits/Procedures	Screening visit	Treatment and Safety Monitoring phase									Follow-up Phase		
		Day 0 (Dose#1)	Day 7 (Dose #2)	Day 14 (Dose #3)	Day 21 (Dose #4)	Day 28	Day 45	Day 56	^a Day 73	Day 180	Day 360	Day 720	
Visit Day	Day -30 to -1												
Visit Window	Day -30 to -1	± 1 day ^b	± 3 days	± 3 days	± 3 days	± 3 days	± 3 days	± 3 days	± 3 days	±28 days	±28 days	±28 days	
Physical Examination	X					X	X	X	X	X	X	X	
Medical & Surgical History	X												
Informed Consent	X												
Active disease on sigmoidoscopy, colonoscopy, or MR enterography	X												
Vital Signs (temp, HR, RR, BP)	X	X	X	X	X	X	X	X	X				
SaO ₂ via pulse oximetry	X	X	X	X	X	X	X	X	X				
AEs/SAEs		X	X	X	X	X	X	X	X				
Concomitant Medications	X	X	X	X	X	X	X	X	X				
Eligibility Criteria		X											
Collection of serum ^c , saliva, urine, stool for research	X	X	X	X	X	X	X	X	X				
Urine pregnancy test (before each infusion)		X	X	X	X								
MSC infusion		X	X	X	X								
Disease activity assessed ^a	X	X	X	X	X	X	X	X	X	X	X	X	
Routine Labs													
CBC	X	X	X	X	X	X	X	X	X				
Electrolytes, liver enzymes, urinalysis	X	X	X	X	X	X	X	X	X				
Quantitative CRP, fecal calprotectin	X	X	X	X	X	X	X	X	X				

BMSCs

^aDisease activity assessed using: PCDAI, PUCAI, CDAI, Mayo, SES-CD

^bOnly applies to routine labs and pregnancy test

^cWe will draw up to 40 ml of blood at 9 time points for research studies (at baseline before the first infusion, before each subsequent infusion, and at the 45 day safety follow up).

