3.8 Treatment Phase (Day 0, 7, 14, 21)

On Days 0, 7, 14, and 21, subjects will arrive at the hospital for infusion of study drug, eligibility criteria, laboratory assessments, assessment of AEs/SAEs, collection of serum, saliva, urine and stool, and assessment of clinical indices.

Safety Monitoring Phase (Day 28, 45, 56, 73) +/- 3 days

During this visit, the patient will return to Children's National, or be seen by a local physician for a follow-up visit, physical exam, laboratory assessments, AEs/SAEs assessment, assessment of clinical indices, bloodwork, saliva, urine and stool collected for fecal calprotectin. Assessment of symptoms and screening for adverse events may be done by telephone if necessary.

Follow-up Phase (Day 180, 360, 720) +/- 28 days

Subjects will return to Children's National, or be seen by a local physician, for a physical examination and assessment of clinical indices. If physical examination is obtained by a local physician, reports will be emailed or faxed to the study investigator. Assessment of symptoms and screening for adverse events may be done by telephone if necessary.

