5.5 RELATIONSHIP TO TREATMENT

The PI or Sub-I must assign a relationship of each AE to the receipt of the investigational product. The investigator will use clinical judgment in conjunction with the assessment of a plausible biologic mechanism, a temporal relationship between the onset of the event in relation to receipt of the investigational product, and identification of possible alternate etiologies including underlying disease, concurrent illness or concomitant medications. The occurrence of adverse events will be monitored at each

visit. The following guidelines should be used by investigators to assess the relationship of an AE to study product administration:

Not related: No relationship to study treatment. Applies to those events for which evidence exists that there is an alternate etiology. For example, events that are clearly related to another medical condition (i.e. diabetes), are related to an outside circumstance (i.e. trauma), or that are not temporally related to administration of the treatment.

Unlikely: Likely unrelated to the study treatment. Likely to be related to factors other than study treatment, but cannot be ruled out with certainty. The need for medical or surgery related to progressive IBD, or known symptoms directly related to IBD such as diarrhea, perianal disease, intra-abdominal or perianal abscess, intra-abdominal fistula, rectal bleeding, and weight loss are unlikely to be related to the study treatment. This also includes patients with known history of extraintestinal manifestations related to IBD (such as arthralgias, arthritis, uveitis, erythema nodosum, pyoderma gangrenosum, or mouth ulcers) who experience such symptoms during the treatment period.

Possible: An association between the event and the administration of study treatment cannot be ruled out. There is a reasonable temporal association, but there may also be an alternative etiology such as the subject's clinical status or underlying factors including other therapy. This includes known potential risks of IBD and treatments that the patient is receiving, such as infection and lymphoma

Probable: There is a high degree of certainty that a relationship to the investigational product exists. There is a reasonable temporal association, and the event cannot be explained by known characteristics of the subject's clinical state or factors including other therapy.

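### The protocol contradicts itself on adverse event collection after Day 73: the schedule marks none at Days 180, 360 and 720, while the text expects it

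*Protocol*

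**What the plan says.** Four parts of the protocol bear on adverse events after Day 73.

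- **Purpose of follow-up.** Section 1.4.2 (Plan of Study) states: "With the additional 24 months of follow up to evaluate longer-term safety and efficacy endpoints", and on that basis puts the trial at about 48 months. Sections 2.2 and 7.1.1 explain the same 24 months by efficacy endpoints alone and do not mention safety.
- **Schedule.** In Table 1 of section 3.6 the row reads "AEs/SAEs X X X X X X X X". The screening cell is empty and the eight marks fall on Days 0, 7, 14, 21, 28, 45, 56 and 73. At Days 180, 360 and 720 only physical examination and disease activity are marked.
- **Follow-up visits.** Under the Follow-up Phase, section 3.8 says that subjects return to the center or may "be seen by a local physician, for a physical examination and assessment of clinical indices". Adverse events are not among the listed assessments. The paragraph then ends: "Assessment of symptoms and screening for adverse events may be done by telephone if necessary".
- **General rule.** Section 5.5 says: "The occurrence of adverse events will be monitored at each" visit, with no end date.

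The formal window is shorter. Section 1.4.2 says: "The safety assessment period will be 45 days from the last dose administered". Section 7.1.4 uses the same 45-day limit for the stopping rules.

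**The concern.** Safety is the primary objective. The primary endpoint in section 2.2.1 is the frequency of any SAEs, AEs or early discontinuations, with no time limit stated. Section 1.4.1 says that safety has not been shown in children with IBD, and section 1.4.2 raises a possible effect on T cell-mediated immunity. Section 5.5 names infection and lymphoma among the events to be classed as possibly related. Some such events could arise after Day 73.

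The schedule of events is usually what sites and data managers build from. Section 8.1.2 says the database captures the assessments required by the protocol and points to a table for them, although the number it cites (4.2.2) belongs to no table in the document. If the forms follow Table 1, there may be no adverse event form at the three late visits. Indirect routes narrow too: section 3.3 stops recording medications and procedures 45 days after the last infusion, and for visits to a local physician section 3.8 asks only that the examination report be sent in.

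With at most six patients, a single late event matters. If collection is uneven, a report of none cannot be interpreted.

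**Working it through.** No sample size, power or error rate depends on this point. The check is of the calendar and of the table.

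1. **Duration.** Inputs: 6 patients at 3 to 4 per year, plus 24 months of follow-up (sections 1.4.2, 2.2 and 7.1.1). Accrual is 6/4 × 12 = 18 months to 6/3 × 12 = 24 months. Total duration is 18 + 24 = 42 to 24 + 24 = 48 months. The protocol's figure of about 48 months is reproduced at the upper end. Day 720 is 720/30.4375 = 23.7 months, so the Day 180, 360 and 720 visits are the visits of this 24-month follow-up.

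2. **Reading of Table 1.** The table has 12 visit columns: screening, eight from Day 0 to Day 73, and three follow-up visits. Because tables can break when read from PDF, rows were compared cell by cell:
   - Disease activity: 12 marks, all visits through Day 720.
   - Physical examination, "Physical Examination X X X X X X X X": 8 marks, at screening, Days 28, 45, 56, 73, 180, 360 and 720, with blank cells at the four infusion visits.
   - Concomitant medications: 9 marks, screening through Day 73.
   - AEs/SAEs: a blank at screening, then 8 consecutive marks, Day 0 through Day 73.

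   The follow-up columns are readable and filled in other rows, so the blanks in the AEs/SAEs row are very unlikely to be a reading fault. Whatever the alignment, 8 marks cannot cover 11 post-screening visits.

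3. **Coverage.** Marked visits: 8 of 11 after screening; 0 of 3 in follow-up. Time from the last mark to the last visit: 720 − 73 = 647 days, or 647/720 = 89.9%. The intervals a late visit would have to cover are 180 − 73 = 107, 360 − 180 = 180 and 720 − 360 = 360 days, which sum to 647.

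4. **Fit to the 45-day window.** With four doses the last is on Day 21, and 21 + 45 = 66; the protocol counts 28 + 45 = 73. Day 73 covers both. If the four optional doses follow without a gap (an assumption), the eighth is on Day 7 × 7 = 49, and the window runs to 49 + 45 = Day 94. That is 21 days past the last AE mark, and the next visit in the table is Day 180.

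5. **Text against table.** Section 1.4.2 (longer-term safety), the closing sentence of the Follow-up Phase in section 3.8, and section 5.5 all imply adverse event collection at Days 180, 360 and 720. Table 1 and the list of follow-up assessments in section 3.8 do not provide it. Sections 2.2 and 7.1.1 drop the safety purpose. These statements cannot all be followed as written.

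**The case against.** A reader might infer from Table 1 that no late adverse event will be recorded and that the longer-term safety aim cannot be met. The documents do not support that, for these reasons:

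- The telephone sentence in section 3.8 is most naturally about the mode of contact. The same sentence appears under the Safety Monitoring Phase, where AE assessment is listed and marked in Table 1, so it cannot make screening optional there. Under follow-up it presupposes screening.
- Section 5.5 requires monitoring at each visit. Section 10.1 has safety monitoring running throughout the study, section 8.1.4 requires the medical record to hold any AEs during the trial, and sections 9.1 and 10.2 provide at least annual safety review by the Data Review Committee. None stops at Day 73. Collection also follows SOPs that are not shown.
- The 647 days are not 647 unobserved days. A visit at Day 180 can ask about everything since Day 73.
- The malignancy described in section 4.1 was found at day 42, inside the monitoring window, so it is no example of a missed late event. Section 5.5 lists infection and lymphoma as risks of IBD and its treatments, not as known late effects of the cells.
- The stopping rules use the 45-day window, which Table 1 covers for the four-dose schedule.

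All of this stands, and it rules out a claim of non-collection. It does not remove the inconsistency: the general provisions say that events are to be monitored and kept, but the visit schedule does not assign the task to the three follow-up visits. The efficacy-only wording in sections 2.2 and 7.1.1 adds a second conflict with section 1.4.2.

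**Conclusion.** The point holds as an internal contradiction. Adverse event collection is marked at none of the three follow-up visits, yet one section gives that follow-up a longer-term safety purpose and two others imply collection there. The practical risk is incomplete and uneven capture of late events. It rests on the assumption that case report forms and site practice follow Table 1, which is plausible but cannot be confirmed without the forms and SOPs.

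The effect on the four-dose toxicity outcome and its stopping rules is nil. The effect on any statement about safety after Day 73 is material: with six patients or fewer, a count of zero would have no clear meaning. The point deserves correction because safety is the trial's primary objective and the remedy is nearly free.

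**What to change.** - In Table 1 of section 3.6, mark AE/SAE collection at Days 180, 360 and 720.
- In section 3.8, list adverse event screening among the follow-up assessments and state that it is done at each follow-up contact, in person or by telephone, covering the time since the last contact.
- Use one statement of the purpose of the 24-month follow-up in sections 1.4.2, 2.2 and 7.1.1.
- Report events after the window that ends 45 days after the last infusion separately from those within it, so that the toxicity outcome is unchanged.
- Correct the table reference in section 8.1.2 so that it points to the schedule of events.

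If the sponsor does not intend to study longer-term safety, the alternative is to remove that purpose from section 1.4.2 and to give the primary endpoint in section 2.2.1 an explicit time limit. That is consistent, but it gives up information from visits that take place anyway.

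The cost of the main change is a few questions at three existing visits, a small change to the case report forms, and the edits above. No sample size or analysis changes.
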